## 4. INTRODUCTION

## 4.1. Background

Attention deficit hyperactivity disorder (ADHD) is a neurodevelopmental disorder characterized by persistent inattention, hyperactivity, and impulsivity that is more severe or frequent when compared to individuals of the same developmental stage. There are a number of characteristics related to cognition that distinguish people with ADHD from people without ADHD including deficits in response inhibition (Aron-2005, Goto-2010, Luna-2004) and reward sensitivity (Passarotti-2011), as well as working memory, attention, planning, and behavioral inhibition (Hervey-2004, Boonstra-2005, Willcutt-2005). ADHD is prevalent in approximately 8% to 10% of school-aged children and approximately 2% to 5% of adults (Ferri-2014). Symptoms experienced in childhood often persist into adolescence and adulthood, though the hyperactivity component tends to diminish over time (Ferri-2014).

The etiology of ADHD is not fully understood, but it is believed that both genetic and non-genetic factors are implicated in the disease. Several factors related to disturbances of neonatal development including premature birth, low birth weight, and perinatal complications have been shown to increase the risk of developing ADHD in childhood (Perricone-2013, Botting-1997, Amor-2005). The neurotransmitters dopamine and norepinephrine, and perhaps to a lesser degree serotonin, are expected to have a critical role in the development of ADHD and thus receptors associated with these are key drug targets (Rader-2009). Changes in serotonergic, cholinergic, and mostly dopaminergic functioning have been documented in children with ADHD (Dopheide-2011).

Current ADHD pharmacotherapies have effects on central catecholamine neurotransmission. In nonclinical microdialysis studies, ADHD drugs like amphetamine, methylphenidate, and atomoxetine increase dopamine and norepinephrine – either by reuptake inhibition or stimulation of release – especially in the prefrontal cortex. At clinically-efficacious doses, 50% dopamine transporter (DAT) occupancies are reported with methylphenidate in adults with ADHD (Volkow-1998).

Adrenergic signaling in the prefrontal cortex is thought to control attentional processes and thus contribute to working memory and executive functions (Arnsten-2011, Gamo-2011). Consistent with this neuronal circuitry, norepinephrine transporter (NET) inhibition (eg, atomoxetine) alone is sufficient for clinical efficacy in ADHD. The stimulants amphetamine and methylphenidate both increase norepinephrine concentrations centrally, and methylphenidate achieves 50% NET occupancy in human subjects at doses clinically efficacious in ADHD (Hannestad-2010).

Dasotraline (also known as SEP-225289) is a new chemical entity that is thought to produce its therapeutic effects in ADHD by inhibition of the presynaptic dopamine transporter (DAT) and NET, as determined by receptor occupancy and microdialysis studies. Pharmacologically, dasotraline is consistent with dopamine and norepinephrine, reuptake inhibitor (DNRI) effects. Dasotraline is a diastereomer of the major metabolite of the selective serotonin reuptake inhibitor sertraline, but is not a metabolite of sertraline, nor is it converted to the desmethylated metabolite of sertraline in vivo. Unlike amphetamines, dasotraline does not increase the release of these monoamines into the extraneuronal space. Dasotraline's pharmacokinetic profile, unique among

ADHD treatments, allows plasma concentrations to remain in a therapeutic range over the 24 hour dosing interval at steady state.

The evaluation of the pharmacokinetics and safety of dasotraline in pediatric and adolescent subjects is currently ongoing (Study SEP360-105). Study SEP360-105 will evaluate the safety, tolerability, pharmacokinetics, and pharmacodynamics of single oral doses of dasotraline in subjects 6-17 years old with ADHD. It is a multicenter, open-label study in which subjects are assigned to study drug in a dose-escalating manner. The doses planned to be evaluated range from 1-32 mg. Additionally, the safety and efficacy of dasotraline in 6-12 year old subjects with ADHD is ongoing in a randomized, double-blind, multicenter, placebo-controlled, parallel-group, outpatient study (SEP360-202).

Further information on nonclinical and clinical studies is provided in the Investigator's Brochure.

As there is a considerable unmet medical need for ADHD medications in children and adolescents that may warrant long-term treatment, Sunovion believes dasotraline, a novel inhibitor of NET and DAT, may be a useful addition to the current treatment armamentarium. Based on the available data dasotraline may provide steady, full-day coverage of DAT and NET inhibition. Dasotraline is being evaluated as a once daily treatment for children, adolescents and adults with ADHD with possible therapeutic coverage across the 24-hour dosing interval.

# 4.2. Study Conduct Rationale

ADHD is prevalent in approximately 8% to 10% of school-aged children (Ferri-2014) and causes substantial impairments in everyday functioning that may warrant long-term treatment. A medication such as dasotraline that may provide therapeutic coverage across a 24-hour dosing interval may prove beneficial for the treatment of ADHD.

This is an open-label extension study to evaluate the safety and effectiveness of flexibly-dosed dasotraline over 26 weeks of treatment in children and adolescents with ADHD who completed 6 weeks of double-blind treatment in Study SEP360-202 (ie, the core study).

## 4.3. Risk-Benefit Assessment

Two studies were recently completed to support dasotraline as a safe and efficacious treatment for adults with ADHD with minimal abuse potential.

The first study, SEP360-201, a randomized, double-blind, parallel-group, outpatient study at 30 sites, evaluated the efficacy and safety of dasotraline in adults with ADHD using 2 doses (4 mg/day or 8 mg/day) versus placebo over a 4-week treatment period. In this study, clinically meaningful treatment effects were observed for both dasotraline 4 mg/day and 8 mg/day compared to placebo. For the primary efficacy endpoint, change from baseline in ADHD RS-IV with adult prompts total score at week 4, statistical significance was achieved for dasotraline 8 mg/day compared to placebo (adjusted p = 0.019) with a strong trend for dasotraline 4 mg/day (adjusted p = 0.076). Efficacy with both doses was observed for the secondary endpoint change from baseline in CGI-S (4 mg group p = 0.021; 8 mg group p = 0.013). A dose response relationship was observed supporting pharmacological activity in ADHD. Decreases in 3, 4-dihydroxyphenylglycol (DHPG) concentrations indicated the presence of central NET inhibition. Treatment-emergent AEs (TEAEs) were consistent with dasotraline pharmacology, ie, insomnia, decreased appetite, dry mouth, and headache. Worsening of insomnia associated with

dasotraline was characterized by TEAEs, and shifts in Insomnia Severity Index (ISI) total score, particularly with dasotraline 8 mg/day. TEAEs, particularly insomnia, were the most frequent reason for discontinuation of dasotraline 8 mg/day. Decreases in mean body weight were generally greater for dasotraline 8 mg/day than 4 mg/day. Increases in mean supine and standing heart rate observed during treatment and follow-up were generally higher on dasotraline 8 mg/day than 4 mg/day.

No signs or symptoms of withdrawal upon discontinuation of dasotraline were observed for either dose. In addition, there was no evidence of drug liking or deterioration of psychiatric symptoms associated with either dose of dasotraline. No misuse or diversion of dasotraline was detected through the abuse potential monitoring plan

A second study, SEP360-101, evaluated dasotraline's abuse liability and was conducted in recreational stimulant users; results indicated that dasotraline has low abuse liability. All doses of dasotraline (8, 16, 36 mg) demonstrated significantly lower drug liking scores than methylphenidate (40, 80 mg) and were no greater than placebo.

Four previous clinical studies in healthy adult subjects using single doses ranging from 0.2 mg to 36 mg and doses of 1 mg/day to 3 mg/day for durations up of 21 days, and 1 study in adult subjects with major depressive disorder (MDD) using doses of 0.5 mg/day and 2 mg/day for up to 8 weeks (56 days) have been completed. In these clinical studies, dasotraline was generally safe and well tolerated at the doses studied and there was no evidence of abuse or diversion and no symptoms of withdrawal.

## 5. STUDY OBJECTIVES

## 5.1. Primary Objectives

To evaluate the long-term safety and tolerability of flexibly-dosed dasotraline in children and adolescents with ADHD by the incidence of adverse events (AEs; or serious AEs [SAEs]), and AEs (or SAEs) leading to discontinuation.

## 5.2. Secondary Objectives

The secondary objectives of the study are:

- To evaluate the long-term safety and tolerability of flexibly-dosed dasotraline in children and adolescents with ADHD by assessing clinical laboratory evaluations, vital signs, physical examinations, body height and weight, 12-lead electrocardiograms (ECG), Tanner Staging, Children's Sleep Habits Questionnaire (CSHQ), and the frequency and severity of suicidal ideation and suicidal behavior using the Columbia – Suicide Severity Rating Scale (C-SSRS) Children's Assessment.
- To assess the long-term effectiveness of dasotraline in children and adolescents with ADHD using the following assessments:
  - the ADHD Rating Scale Version IV Home Version (modified for investigator administration) (ADHD-RS-IV HV)
  - the Clinical Global Impression Severity (CGI-S)
  - the Conners 3rd Edition Parent (Conners 3-P)
- To evaluate health-related quality of life and functional impairment in children and adolescents with ADHD using the Weiss Functional Impairment Rating Scale Parent Report (WFIRS-P).
- To assess potential withdrawal symptoms following discontinuation of dasotraline treatment using the following assessments (administered during the withdrawal period):
  - Discontinuation-Emergent Signs and Symptoms (DESS) Scale
  - Physician Withdrawal Checklist (PWC)

## 6. STUDY ENDPOINTS

## 6.1. Primary Endpoint

The incidence of overall AEs (or SAEs), and AEs (or SAEs) leading to discontinuation.

# 6.2. Secondary Endpoints

The secondary endpoints are:

- Clinical laboratory evaluations (serum chemistry, hematology, lipid panel, thyroid function panel, urinalysis, sex hormones).
- Clinical evaluations (vital signs, physical examination, body height and weight, Tanner Staging, and 12-lead ECG).
- Frequency and severity of suicidal ideation and suicidal behavior using the C-SSRS.
- Change in CGI-S score.
- Change in ADHD-RS-IV HV total score.
- Change in the inattentiveness and hyperactivity subscales of the ADHD-RS-IV HV.
- Change in Conners 3-P total score and subscale scores (Oppositional, Cognitive problems, Hyperactivity, and ADHD Index).
- Change in CSHQ total score and 8 subscale scores (bedtime resistance, sleep onset delay, sleep duration, sleep anxiety, night wakings, parasomnias, sleep disordered breathing, and daytime sleepiness).
- Change in WFIRS-P total score and 6 domain scores (family, school learning behavior, life skills, child's self-concept, social activities, and risky activities).
- Symptoms of withdrawal using:
  - PWC score
  - DESS score

## 7. INVESTIGATIONAL PLAN

## 7.1. Overall Study Design

This is an open-label, flexibly-dosed, 26-week extension study in children and adolescents with ADHD who have completed 6 weeks of double-blind treatment in the core study. This study will evaluate the long-term safety and tolerability of dasotraline in this population. In addition, several measures of effectiveness will be included. Subjects who have completed the core study (ie, completed Week 6 visit) will be eligible to enroll in this extension study; subjects who discontinue from the core study will not be eligible to enroll in this study. Subjects will be evaluated for eligibility in this extension study during the Week 6 visit of the core study. Informed assent by the subject and informed consent from at least one of the subject's parents or legal guardians will be obtained before any study procedures are performed for this study.

Subjects who meet all eligibility criteria will transition directly from the core study and will not need to complete the End of Study (EOS) visit in the core study. Subjects will take the first dose of open-label study drug in this extension study on Day 1, the morning following the open-label (OL) Baseline visit. Subjects will continue to take study drug for 26 weeks, at approximately the same time each morning including on the days when clinic visits occur. Dasotraline will be dosed at 2 mg/day for the first week of the study (Days 1 - 7). Subjects will then be flexibly dosed (2, 4, or 6 mg/day) thereafter beginning on Day 8 based on the investigator's assessment of effectiveness and tolerability. All changes in study drug dose will begin the morning after the visit at which the dose change decision is made using the new package of study drug. Additional dose adjustment is allowed during the study at the discretion of the investigator; the dose may be increased or decreased by 2 mg/day, as necessary for effectiveness or tolerability reasons. Total daily dose will not exceed 6 mg/day. There is no limit on the number of dose increments or reductions during the study. A minimum of 7 days is required between dose increases. Dose decreases may be made at less than 7 day intervals for safety/tolerability reasons, at the investigator's discretion. Subjects wishing to take study drug at an alternate time of day require investigator and medical monitor approval.

After the OL Baseline visit, subjects will return to the clinic weekly for the first 2 weeks, once every 2 weeks for the next 4 weeks, then once every 4 weeks for the remainder of the treatment period for clinical evaluation, and once at the end of the withdrawal period (Visit 13E). At the approximate midpoint between the scheduled monthly visits (ie,  $14 \pm 2$  days after a visit) during the treatment period, the site staff will contact the subject's parent/legal guardian via telephone, text, or email in order to evaluate the safety of the subjects as well as to remind subject/parent/legal guardian about adherence to study drug administration and upcoming visits, following which, if necessary, an unscheduled visit can be arranged.

Safety and tolerability will be monitored throughout the study by collection of AEs, clinical laboratory evaluations, vital signs, physical examinations, body height and weight, 12 lead ECG, Tanner Staging, CSHQ, and the frequency and severity of suicidal ideation and suicidal behavior using C-SSRS. The measures of effectiveness, ADHD-RS-IV HV, CGI-S, and Conners 3-P, and assessment of health-related quality of life and functional impairment, WFIRS-P, will be completed as scheduled (Table 2).

A Data and Safety Monitoring Board (DSMB) will review safety and clinical outcome data including data on AEs and serious AEs at regular intervals.

[figure not shown]
Assessment of potential withdrawal effects will be conducted via administration of the DESS and PWC at the end of study drug treatment (Visit 10E) and upon the completion of the withdrawal period (Visit 13E). In addition, the subject/parent/legal guardian will be called by the clinical site staff once a week (Day  $189 \pm 3$  and Day  $196 \pm 3$ ) during the withdrawal period to complete the DESS. Phone contacts may be made up to 3 times per day if the clinical site staff is unable to contact the subject/parent/legal guardian on the first 2 attempts. If the subject/parent/legal guardian cannot be contacted on a given day, during the next contact the study site staff will retrospectively collect the missed DESS, in addition to the current day's DESS, as necessary. Clinical site staff will record the responses in the subject's source information and in the CRF with the contact date and time. As noted above, all subjects will return to the clinic 3 weeks ( $\pm$  7 days) after the final dose of study drug for withdrawal (DESS and the PWC) and EOS safety assessments (Visit 13E).

Subjects who discontinue from the study prior to completion will be asked to return to the clinical site and complete the Early Termination assessments within 3 days of discontinuation and complete all withdrawal period assessments (calls) and EOS visit.

After the EOS visit or upon discontinuation of study drug, all subjects will be referred for continuation of their care as determined by the investigator.

A study schematic is presented in Figure 1. Details of the study assessments and other procedures to be performed at each visit are presented in Table 2 Schedule of Assessments, and Section 11, Study Assessments.

Figure 1: Study Schematic

<sup>a There will be no break in study drug treatment between the core study and this extension study .

## 7.2. Rationale

## 7.2.1. Rationale for the Study Design

This is an open-label study to evaluate the long-term safety and effectiveness of flexibly-dosed dasotraline consistent with the intended long-term use of the compound in this population.

<sup>b Dasotraline will be dosed at 2 mg/day for the first week of the study (Days 1 - 7). Subjects will then be flexibly dosed (2, 4, or 6 mg/day) thereafter beginning on Day 8 based on the investigator's assessment of effectiveness and tolerability.

## 7.2.2. Rationale for the Dosages

Given the similarities observed in pharmacokinetics between adult and pediatric subjects, predictions from a population pharmacokinetic (PK) model of dasotraline previously established in adult subjects were evaluated against the observed single-dose pharmacokinetics in pediatric subjects enrolled in Study SEP360-105. Model predictions of the observed dasotraline single-dose pharmacokinetics in Study SEP360-105, using subjects (smaller) body sizes in the combined population PK model, corresponded well with the observed pharmacokinetics in Study SEP360-105. Thus, available dasotraline concentration data collected from pediatric subjects enrolled in Study SEP360-105 (1, 2, 4, and 8 mg cohorts, ages 6 to 17 years old) were pooled together with the previously developed population PK dataset and when the model was re-evaluated good model fit was demonstrated for all subjects encompassing a broad range of body sizes.

The dose range to be used in this study (2, 4, and 6 mg/day) was selected based on evaluation of data from a combined dasotraline population pharmacokinetic (PK) model. This analysis demonstrated that the model-based predictions for dose-exposure distributions in pediatric subjects for the doses of 2 mg/day and 4 mg/day fall within the dose-exposure distributions observed for adults following treatment with dasotraline 4 mg/day and 8 mg/day, which demonstrated clinically significant efficacy after 4 weeks of treatment in an adult ADHD population. The 6 mg/day dose was included to allow for flexibility of dosing in this long-term trial and to evaluate the safety and tolerability of this dose in the pediatric population. Dasotraline has been shown to be generally safe and well-tolerated at equivalent doses in adults.

All subjects in the current study will initially be started at 2 mg/day and then be flexibly dosed (2, 4, or 6 mg/day) thereafter.

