#### 15. STATISTICS

The Statistical Analysis Plan (SAP) will provide details on the statistical methods planned for this study and will be finalized before database lock (DBL).

All statistical summaries will be presented by treatment group from the double-blind core study as well as all subjects in the extension study.

Changes from baseline in safety and effectiveness endpoints will be calculated from both the double-blind (DB) baseline in the core study and the open-label (OL) baseline in the extension study, which is the Week 6 endpoint in the core study for most measures. No statistical inference will be performed for treatment comparison as this is a single arm, open-label, extension study.

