6. GENERAL ASPECTS FOR STATISTICAL ANALYSIS

6.1. GENERAL METHODS

- All analyses and summaries will be produced using SAS[®] version 9.3 (or higher) for windows.
- All statistical summaries will be presented based on the treatment received in the double-blind core study (SEP360-202), called DB treatment. Because the treatment received in SEP360-310 is flexible, the treatment groups for summary in SEP360-310 will be labeled as:
 - placebo / dasotraline flexible,
 - dasotraline 2 mg/day / dasotraline flexible,
 - dasotraline 4 mg/day / dasotraline flexible,
 - dasotraline combined / dasotraline flexible, and
 - total.
- The dasotraline combined group will include those subjects who were treated in SEP360-202 with dasotraline 2 mg/day and dasotraline 4 mg/day.
- Summaries will also be presented by visits (Double-Blind Baseline, Open-Label Baseline, Weeks 1, 2, 4, 6, 10, 14, 18, 22, 26, Week 26 or Treatment Period LOCF,

and EOS). See the details for the DESS and PWC for discussion of the display of visits for those summaries.

- Unless otherwise specified, continuous variables will be summarized with descriptive statistics including: n, arithmetic mean, standard deviation (SD), 95% confidence interval for the mean, median, minimum, and maximum values. All categorical/qualitative data will be presented using frequency counts and percentages. Shift tables will be produced for some assessments and will contain counts and percentages of subjects in each cross-classification level of baseline versus post-baseline assessment. Only subjects with a non-missing value for both baseline and post-baseline, at a given visit, will be included in these tables.
- The listings will be provided using the enrolled population (defined in [Section 8.1](#)). For listings related to analyses conducted using the intent-to-treat population, a flag will be shown in the subject column identifying subjects who were excluded from the intent-to-treat population. In general, the subject listings will be sorted by the treatment group, subject number and assessment date (and time, if applicable).

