The summary will also include the average daily dose (mg) for all subjects, the average daily dose (mg) for subjects who complete the study, the modal daily dose (mg) for all subjects, and the modal daily dose (mg) for subjects who complete the study. The modal daily dose will also be reported for each visit. The average daily dose is calculated as $[(2 \times \text{number of days 2 mg was taken}) + (4 \times \text{number of days 4 mg was taken}) + (6 \times \text{number of days 6 mg was taken})] / (\text{date of last dose} - \text{date of first dose} + 1)$. For each subject the modal daily dose is defined as the dose taken most frequently. Unscheduled visits will also be considered in the calculations when reporting data at each visit. If 2 or more different doses were taken an equal number of days, then modal

dose will equal the dose that the subject last takes. The number of days each dose was used will be summarized. Also, the total person-years during SEP360-310 will be summarized. The total person-years is defined as the sum of the duration of dosing in days for all subjects divided by 365.25.

A bar chart will summarize the percentage of subjects taking 2 mg, 4 mg, and 6 mg at each visit.

A summary will also be provided for the changes in dose from the previous visit. Categories that will be summarized include: maintained dose at 2 mg, down-titrated to 2 mg, up-titrated to 4 mg, maintained dose at 4 mg, down-titrated to 4 mg, up-titrated to 6 mg, maintained dose at 6 mg. Data from unscheduled visits will also be considered when assigning categories. The category will represent the change from the most recent visit. If the dose was changed during an unscheduled visit, then the category will represent the change from the most recent unscheduled visit.

Treatment compliance will be determined for each subject at each visit and over all visits. A descriptive summary will be provided.

Compliance = (Capsules Dispensed - Capsules Returned)*100/Capsules Expected. Subjects are expected to take 1 capsule per day. Only visits with both capsules dispensed and capsules returned will be included. For overall compliance if the number of capsules returned is missing for one or more visits for a subject, then overall compliance will be considered missing for that subject.

Subjects who take less than 75% of scheduled doses or who take more than 125% of scheduled doses will be considered noncompliant.

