12.1. ADVERSE EVENTS (AEs)

The summary of AEs (or SAEs) will be limited to TEAEs. A TEAE is any AE (or SAE) occurring on or after the date of the first dose of study drug in the SEP360-310 study. All AEs will be coded using MedDRA version 19.0.

TEAEs will be further divided into:

- 1.) Those events with onset between the date of the first dose of study drug in the SEP360-310 study and 3 days after the last dose of study medication in SEP360-310, inclusive. These will be called on treatment events.
- 2.) Those events with onset more than 3 days after the last dose of study medication in SEP360-310. These will be called post-treatment events.

AEs with preferred terms of “Insomnia”, “Initial insomnia”, “Middle insomnia”, or “Terminal insomnia”, or AEs with Higher Level Term of “Disturbances in initiating and maintaining sleep” will be presented on AE tables in a combined term called “Combined insomnia” with the individual preferred terms within the combined term directly underneath.

All TEAEs will be summarized by SOC and PT. Though only TEAEs will be included in the summary tables, all AEs will be included on the listings (non-TEAEs will be flagged).

An overall summary table of TEAEs by DB treatment will be produced for the following categories:

- Number and percentage of subjects with a TEAE
- Number and percentage of subjects with a treatment-related TEAE
- Number and percentage of subjects with a TEAE leading to discontinuation
- Number and percentage of subjects with a Treatment-related TEAE leading to discontinuation
- Number and percentage of subjects with a serious TEAE
- Number and percentage of subjects with a serious TEAE leading to discontinuation
- Number and percentage of subjects with a treatment-related serious TEAE
- Number and percentage of subjects with a Treatment-related serious TEAE leading to discontinuation
- Number and percentage of subjects with a TEAE leading to death

This overall summary will be repeated for each onset period. For the post-treatment events, the denominators will be the number of subjects in each DB treatment group whose end of study visit was more than 3 days after the last dose date.

Subgroup analyses of the above noted TEAE categories will be produced for the following subgroups (sex, race (categorized as White, Black or African American, Asian, and Other), DB baseline age group (6-9 vs. 10-12 years)).

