Adverse events will be summarized by DB treatment and overall for subjects in the safety population. The following summaries of AEs will be provided:

- TEAEs by SOC and PT
- TEAEs by PT
- TEAEs by PT ($\geq 3\%$ in any DB treatment group)
- Serious TEAEs by SOC and PT
- TEAEs leading to discontinuation by SOC and PT
- TEAEs by SOC and PT and maximum severity. Missing severity, if any, will be assumed as 'severe'.

- TEAE by relationship to study treatment (related or not related) by SOC and PT. Missing relationships, if any, will be assumed to be ‘related’.
- Treatment related SAEs by SOC and PT

The prevalence of Insomnia by study day in the study will be presented graphically by DB treatment and overall. Combined insomnia events will be used for this analysis. On any study day, the numerator will be the number of subjects who were experiencing insomnia (noting that subjects may have experienced multiple episodes during the study), and the denominator will be the number of subjects remaining on open-label study drug treatment.

The following listings of AEs will be provided:

- All AEs
- Adverse events leading to discontinuation of study drug
- Serious adverse events

In the summary tables subjects may be counted under multiple SOC and PTs, but for each SOC and PT, subjects are only counted once. If a subject has the same AE on multiple occasions, the highest severity (severe, moderate, mild) recorded for the event will be presented and the highest drug relationship (1 = ‘Unrelated’, 2 = ‘Unlikely to be Related’, 3 = ‘Possibly Related’, 4 = ‘Probably Related’, 5 = ‘Related’), reclassified into Related (‘Possibly Related’, ‘Probably Related’, ‘Related’) or Not Related (‘Unrelated’ and ‘Unlikely to be Related’), will be presented on the respective tables. Percentages are based on the number of subjects in the safety population.

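### Evaluating the safety of 6 mg/day is a stated reason for including that dose, but no safety outcome in the SAP is summarised by open-label dose

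*Protocol*

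**What the plan says.** Protocol 7.2.2 explains the 2, 4 and 6 mg/day range. It includes 6 mg/day for flexibility and "to evaluate the safety and tolerability of this dose in the pediatric population".

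The grouping rule is the same in both documents. Protocol 15: "All statistical summaries will be presented by treatment group from the double-blind core study as well as all subjects in the extension study". SAP 6.1: "All statistical summaries will be presented based on the treatment received in the double-blind core study (SEP360-202), called DB treatment". The SAP columns are placebo, 2 mg, 4 mg, a combined group and a total. The combined group is defined so: "The dasotraline combined group will include those subjects who were treated in SEP360-202 with dasotraline 2 mg/day and dasotraline 4 mg/day". No column is defined by 6 mg.

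SAP 12.1 applies the rule to the primary endpoint: "An overall summary table of TEAEs by DB treatment will be produced for the following categories", and "Adverse events will be summarized by DB treatment and overall for subjects in the safety population". Its further splits are demographic: "Subgroup analyses of the above noted TEAE categories will be produced for the following subgroups (sex, race" and double-blind baseline age group), together with onset on or after treatment.

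Open-label dose is used in SAP 10.4 only, for example "The number of days each dose was used will be summarized". That section also gives average and modal dose, the percentage of subjects on each dose by visit, and categories of dose change since the previous visit.

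**The concern.** The protocol names a question about one dose, and the analysis plan has no table that takes it up. All subjects start at 2 mg/day and move between doses at the investigator's discretion (Protocol 10.2). The core-study arm therefore says little about the dose a child was taking when an event began. Events that arise at 6 mg are counted in the same columns as events at 2 and 4 mg.

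Dose could matter here. In the adult ADHD study described in Protocol 4.3, worsening of insomnia was noted particularly at 8 mg/day, and weight loss and heart-rate increases were generally larger at 8 than at 4 mg/day. If a similar gradient existed in children, the planned tables would blur it.

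**Working it through.** The plan gives no figure to reproduce. The sample size (Protocol 15.1, SAP 4.2) is up to 330 subjects, set by roll-over from the core study, with no power or precision target. The check is a reading of each output's grouping variable, followed by three short calculations.

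**1. Grouping of each safety output**

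| Output | SAP section | Grouping | Further split |
|---|---|---|---|
| TEAEs | 12.1 | Core arm, total | Sex, race, age group, onset period |
| Laboratory | 12.2 | Core arm, total | None by dose |
| ECG, QTc | 12.5 | Core arm, total | Age (marked abnormalities) |
| Neurological examination | 12.7 | Core arm, total | None by dose |
| Vital signs | 12.8 | Core arm, total | None by dose |
| C-SSRS, CSHQ | 12.9, 12.10 | Core arm, total | None by dose |
| Tanner staging | 12.11 | Core arm, total | Gender |
| PWC, DESS | 12.12, 12.13 | General rule in 6.1 | Gender |
| Exposure | 10.4 | Core arm, total | Open-label dose |

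Safety outcomes summarised by current, modal, maximum or at-onset dose: none.

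**2. How mixed each column is.** Treatment runs from Day 1 to Day 182, with 2 mg on Days 1 to 7. On the nominal schedule, 2 mg steps at least 7 days apart put the earliest 6 mg day at Day 15, so time at 6 mg is at most 182 − 15 + 1 = 168 days (168/182 = 92%). If 6 mg were taken directly from Day 8, the maximum is 182 − 8 + 1 = 175 days (96%). No subject is on 6 mg throughout, so every column mixes doses.

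**3. Dilution, with assumed risks.** Let risk be 10% below 6 mg and 20% at 6 mg, with a share f of subjects at 6 mg. The pooled risk is 0.20f + 0.10(1 − f):

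- f = 10%: 11.0%
- f = 25%: 12.5%
- f = 50%: 15.0%

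The 20% cannot be recovered from the pooled figure alone.

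**4. What a by-dose table could support, with an assumed number on 6 mg.** With zero events in n subjects, the one-sided 95% upper bound is 1 − 0.05^(1/n):

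- n = 66 (20% of 330): 4.4%
- n = 165 (50% of 330): 1.8%

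Over a wider assumed range, n = 33 (10%) gives 8.7% and n = 248 (75%) gives 1.2%. These bounds count subjects and ignore unequal time on the dose.

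**The case against.** Several points on the other side stand and limit what can be claimed.

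- A reader might infer that the trial cannot meet its purpose. The documents do not support that. The objectives and primary endpoint (Protocol 5.1 and 6.1, SAP 3.1 and 5.1) concern flexibly-dosed dasotraline and overall AE incidence, and the planned tables answer them. The reference to 6 mg is half of one sentence in the dose rationale.
- A reader might infer that nothing at all will be reported about 6 mg. That is also too strong. SAP 12 counts exposure as part of safety, and SAP 10.4 reports days on 6 mg and the percentage on it by visit. Its category for down-titration to 4 mg can only mean coming down from 6 mg. This is an indirect tolerability signal, with no event or reason attached.
- A reader might infer that no bound could be stated for 6 mg. An event with no cases in the total column has none at 6 mg either, so it could be bounded if the exposure table shows how many took 6 mg. The gap concerns events also seen at other doses.
- A reader might infer that 6 mg lacks support. Protocol 7.2.2 states adult exposure matching for 2 and 4 mg only, but it also says the whole range came from the PK model, pools data from an 8 mg single-dose paediatric cohort, and refers to tolerability at equivalent adult doses.
- Adverse events are listed by subject, and the listing shells are attachments not available here. A dose column in a listing cannot be ruled out, though the SAP text specifies none.

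The strongest objection is to the remedy. Children who reach and stay on 6 mg have tolerated lower doses. Everyone takes 2 mg in Week 1, including those who received 4 mg in the core study, so early events fall to 2 mg. Crude by-dose rates could make 6 mg look safer than it is. This is a reason for careful construction and labelling. It does not justify omission from a study that draws no inference anyway.

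**Conclusion.** The gap is real and limited. The protocol states a reason for including 6 mg/day, and no planned safety outcome is tied to that dose. The two documents agree with each other on grouping, the primary analysis stands, and no dose or clinical rule is in question. What is missing is a descriptive summary that would let the report speak to the stated reason for 6 mg when an event occurs at more than one dose.

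Its size cannot be fixed from the documents, because the share of subjects reaching 6 mg is not given and 330 is a ceiling. The 4.4% to 1.8% range is an illustration of the precision available under an assumed 66 to 165 subjects on 6 mg. It does not measure the harm done by the omission. The change should be made before the SAP is finalised, since choosing how to attribute events to doses after seeing the data would be less credible.

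**What to change.** In SAP 12.1 add descriptive TEAE tables by dose at onset (2, 4, 6 mg): overall summary, common preferred terms, combined insomnia, serious events, and events leading to discontinuation. For each dose show the number of subjects ever on it and the person-years on it, and use both as denominators. Days on each dose are already derived in SAP 10.4.

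State an attribution rule for events that begin soon after a dose change. The rule should also cover partial onset dates: SAP Appendix 3 sets a wholly missing AE start date to the date of first dose, which would place such events at 2 mg by default.

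In SAP 12.5 and 12.8, summarise QTc outliers and markedly abnormal vital signs by dose at the visit.

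Footnote these tables to say that dose was chosen on tolerability and effectiveness and that all subjects take 2 mg in Week 1, so no between-dose inference is drawn. If the sponsor prefers not to add them, Protocol 7.2.2 should no longer give evaluation of 6 mg as a purpose.

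The cost is SAP wording and a few extra tables, with no new data collection. The downside is that the rates remain confounded by titration and may make 6 mg look safer than it is.
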